5.2.2. Prohibited Concomitant Medications

Pirfenidone and nintedanib are permitted as approved IPF therapies, if clinically indicated during the study. For details, see Section 5.1.10.

Prohibited medications include any other (off-label or investigational) agents for the treatment of interstitial lung diseases including IPF. The list of prohibited concomitant medications for treatment of IPF includes, but is not limited to, the following:

- sildenafil: if used for erectile dysfunction the frequency of administration should be no more than two times a week,
- azathioprine,
- cyclophosphamide,
- cyclosporine,
- interferon gamma 1b,
- D penicillamine,
- methotrexate,
- leflunomide,
- colchicine,
- bosentan,
- ambrisentan,

- aminobenzoate,
- mycophenolate mofetil,
- imatinib,
- relaxin,
- etanercept,
- adalimumab,
- infliximab,
- anakinra,
- abatacept,
- rituximab

If any of these treatments are prescribed for their approved indications, for other co-existing medical conditions such as systemic inflammatory diseases (e.g., rheumatoid arthritis, severe pulmonary hypertension, etc.), such uses are allowed. All indication needs to be clearly documented in the subject's clinical record.

Questions about concomitant medications should be discussed with the FibroGen Medical Monitor.

5.2.3. Contraception Requirements

A non-clinical study evaluating the potential effects of pamrevlumab on embryo-fetal development has been conducted (rabbit embryo-fetal development study 352021017). The pamrevlumab systemic exposure levels at 200 mg/kg to the pregnant female rabbits which resulted in fetal external and skeletal abnormalities are approximately 20-fold greater than the systemic exposure levels in humans at doses of 30 mg/kg or 35 mg/kg in our current protocols.

No adverse effects of pamrevlumab administration were observed in a study of rat male and female fertility. Lacking information from clinical studies, female subjects of childbearing potential and male subjects who have partners with reproductive potential are required to use a highly effective method of contraception per Clinical Trial Facilitation Group (CTFG) recommendation (for reference see section 13) during the study and for 3 months after the last dose of study drug as follows :

- Combined (estrogen and progestogen containing) hormonal contraception associated with inhibition of ovulation¹:
 - oral
 - intravaginal
 - transdermal

- Progestogen-only hormonal contraception associated with inhibition of ovulation¹:
 - oral
 - injectable
 - implantable²
- Intrauterine device (IUD)²
- Intrauterine hormone-releasing system (IUS)²
- Bilateral tubal occlusion²
- Vasectomised partner^{2,3}
- Sexual abstinence⁴

In each case of delayed menstrual period (over one month between menstruations) confirmation of absence of pregnancy is strongly recommended. This recommendation also applies to women of childbearing potential with infrequent or irregular menstrual cycles.

¹*Hormonal contraception may be susceptible to interaction with the IMP, which may reduce the efficacy of the contraception method (see section 4.3 of the CTGF guidance document).*

²*Contraception methods that in the context of the CTGF guidance are considered to have low user dependency.*

³*Vasectomised partner is a highly effective birth control method provided that partner is the sole sexual partner of the WOCBP trial participant and that the vasectomised partner has received medical assessment of the surgical success.*

⁴*In the context of the CTGF guidance sexual abstinence is considered a highly effective method only if defined as refraining from heterosexual intercourse during the entire period of risk associated with the study treatments. The reliability of sexual abstinence needs to be evaluated in relation to the duration of the clinical trial and the preferred and usual lifestyle of the subject.*

6. ASSESSMENTS OF EFFICACY

6.1. Study Assessments

A signed and dated IRB/IEC-approved informed consent must be obtained before any study-specific assessments are performed. Assessments that are part of routine care are not considered study-specific and may be used at screening to determine eligibility. All subjects will be screened for eligibility before randomization. Only eligible subjects will be randomized into the study.

6.1.1. Screening Period

All screening procedures must be performed within 6 weeks. Plans to rescreen a subject should be discussed with the medical monitor. Study procedures to be performed during the screening period can be found in the SOA (Appendix 1).

6.1.2. Treatment Period

The study procedures and assessments are presented for the Treatment phase in [Appendix 1](#).

The treatment period begins on Day 1 (first study drug infusion) and continues through Week 48. Visit windows are within ± 7 days of the scheduled visit date for Weeks 3 through 48; however, visits should be at least 10 days apart, to ensure intervals of at least 10 days between study drug infusions. The visit window of ± 7 days also applies to assessments that cannot be performed on the same day; these assessments are considered part of that specific visit, and are to be labelled as such.

Subjects who complete the Week 48 visit may be eligible to participate in an optional OLE period where all subjects are offered continuing access to pamrevlumab treatment. The details of procedures and assessments, including visit window for OLE are described in Appendix 6.

6.1.3. Safety Follow-Up

Safety assessments will be performed at the following two time points:

- 28 days after last dose
- 60 days after last dose: follow-up phone call, for a final safety assessment

The visit windows for the safety assessments are: 28 days ± 7 days and 60 days ± 7 days (phone call) after the last dose.

After this protocol-required reporting period, the Investigator does not need to actively monitor subjects for SAEs. However, if the Investigator becomes aware of an SAE/death that may be possibly related to study treatment after the protocol-required reporting period, the Investigator may report the event to FibroGen as outlined in [Section 7](#). SAEs reported outside of the protocol-required reporting period will be captured within the safety database only as clinical trial cases for the purposes of expedited reporting.

6.1.4. Early Study Termination Visit

Subjects who terminate / withdraw from the study early, for any reason, will have an Early Study Termination (ET) visit as soon as feasible. Study procedures to be performed during the ET visit can be found in the SOA (Appendix 1). At the ET visit, PFTs and questionnaires do not have to be repeated, if the last one was performed within 8 weeks of this visit; HRCT does not have to be repeated, if the last one was performed within 4 months of this visit. These subjects will have a safety follow up visit 28 days after the last dose. A follow-up phone call 60 days after last dose will also be completed for a final assessment of safety.

In addition, these subjects should be contacted by phone for vital status at weeks 24 and 48. These subjects will not be eligible for the OLE phase.

6.1.5. Missed Visits

Scheduled visit dates are determined from the time of the first dose, which is defined as Day 1. Protocol-defined visits conducted outside the study visit window (see Section 6.1.2) will be recorded as a protocol deviation unless there is an AE/SAE/intercurrent illness or other extenuating circumstance (such as during the COVID-19 pandemic), resulting in “missed” visit(s). Refer to [Section 5.1.8](#) for additional details. For missed visits, the subject will be asked to resume the planned visit schedule at the next scheduled visit.

NOTE: In accordance with FDA/ EMA Guidance: During the COVID-19 pandemic, the visit modality (e.g.: in-person versus remotely) and scheduling may be adjusted and conducted at the discretion of the Investigator, in accordance with the site’s rules and recommendations, and using all necessary precautions. If a visit has to be done remotely, it can be conducted with any technology available to the site and study subjects, such as via tele-health visits, phone calls, etc.

Subjects who do not receive all study drug doses, but complete the Week 48 visit, are considered study completers, and may be considered for participation in the OLE of pamrevlumab (see also Appendix. 6).

6.1.6. Unscheduled Visits

Unscheduled visits/assessments may be scheduled as needed. Unscheduled visit data will be captured accordingly in the clinical database.

Unscheduled assessments (PFT/HRCT/PRO/Labs): if these assessments are not done / on a scheduled visit, or if a subject misses a visit with these scheduled assessments, they should be performed as unscheduled assessments at the next scheduled visit.

If the subject is unable to perform any assessments at the Week 48 visit, the subject must have an unscheduled visit at the nearest possible date to perform any missed Week 48 assessments.

NOTE: In accordance with FDA/ EMA Guidance: During the COVID-19 pandemic, the visit modality (e.g.: in-person versus remotely) and scheduling maybe adjusted and conducted at the discretion of the Investigator, in accordance with the site’s rules and recommendations, and using all necessary precautions. If a visit has to be done remotely, it can be conducted with any technology available to the site and study subjects.

6.2. Assessments

Refer to the SOA ([Appendix 1](#)) for details regarding the timing and frequency of study assessments. Spirometry, laboratory evaluations and patient reported outcomes assessments should be performed prior to infusions.

6.2.1. Vital Signs (including Weight and Height)

Vital signs to be collected include; heart rate, blood pressure and temperature:

- Heart rate should be collected as beats/min
- Systolic and diastolic blood pressure should be collected from subjects in seated position (mmHg)
- Temperature should be taken as oral or tympanic and captured as °F or °C

Weight is collected during screening, Day 1 and every 12 weeks thereafter. Height is collected during screening only.

6.2.2. Physical Exam

Full physical exams (PEs) will be performed according to the SOA ([Appendix 1](#)). In addition, PEs may be performed throughout the study as needed, if clinically indicated.

6.2.3. Electrocardiogram (ECG or EKG)

12-lead ECGs will be performed in accordance with institutional standards and according to the SOA ([Appendix 1](#)). In addition, ECGs may be performed throughout the study as needed, if clinically indicated.

6.2.4. Laboratory Evaluations

Details regarding sample collection, preparation and transport can be found in the central lab manual.

6.2.4.1. Central Laboratory Evaluations

The following labs will be evaluated by a central laboratory in accordance with the SOA ([Appendix 1](#)):

Table 2: Laboratory Tests

CBC:	Chemistry Panel:
Absolute neutrophil count (ANC)	Bicarbonate
Eosinophils	BUN
Erythrocyte count (RBC)	Calcium
Hematocrit %	Creatinine
INR	Chloride
PT/PTT	Magnesium
Hemoglobin	Glucose
WBCs (Leukocyte count)	ALP
Lymphocytes	ALT
Mean corpuscular volume	AST
Monocytes	Bilirubin, total
Neutrophils	Albumin
Platelets	Phosphorous
Basophils	Potassium
	Sodium
	Cholesterol
	Total Protein
	GGT
	Triglycerides
Pregnancy Test: Urine; Serum hCG at screening and to confirm a positive urine test	
Abbreviations: ALP = alkaline phosphatase; ALT = alanine aminotransferase; AST = aspartate aminotransferase; GGT = Gamma-glutamyltransferase; BUN = blood urea nitrogen; CBC = complete blood count; INR = international normalized ratio; PT/PTT = prothrombin time/partial thromboplastin time; RBC = red blood cell; WBCs = white blood cells; hCG =Human chorionic gonadotropin	

Central lab results obtained during the screening period will be used to determine subject eligibility for participation in the trial. Central lab results will be reviewed by the Investigator for clinical significance and to determine appropriate reporting of adverse events (see [Section 7.3](#)). A Central Laboratory Manual with instructions on specimen collection, processing, storing, and shipping to the central laboratory will be provided to all participating sites.

Local laboratory assessments are not required for this study, but the results of any local laboratory assessments may be used to assess subject safety. If a local lab abnormality is reflective of an AE, report the etiology, if known, as per section 7.3.7. Local laboratory results will not be captured in the clinical database.

NOTE: Local laboratory assessments may also be used in case of Central Laboratory supply shortages or shipment delays. If local laboratory assessments are used instead of central labs, the following points need to be considered:

- In case of local screening labs, the Investigator needs to review the results with respect to Exclusion #10.
- For on-study laboratory assessments, only laboratory abnormalities that are considered clinically significant in the Investigator's assessment need to be reported as TEAEs, as per Protocol Section 7.3.7. In such a case, if possible, the etiology of a lab abnormality should be reported as TEAE, not the abnormal lab value.
- For specialty labs, please collect HAHA samples according to the SOA in Appendix 2 using local supplies while processing/storing these samples as described in the ICON lab manual. Other specialty samples (PK, Biomarkers, Genomic and CTGF) will not be required if local labs are being used

Note: For Czech Republic only, Tuberculosis (TB) screening test to be done using site local lab, if this test was not performed within 6 months prior to screening per study exclusion criteria 23.

6.2.4.2. Pharmacokinetics (PK) and Pharmacodynamics

Additional samples will be collected to evaluate PK, HAHA, HAHA-NA, CTGF, exploratory biomarkers and genomics in accordance with the SOA in [Appendix 2](#). The central laboratory will manage the storage of these samples while analysis will be performed at a specialty lab.

6.2.4.2.1. Pharmacokinetics (Optional)

An optional PK assessment will be performed in a subset of subjects at select sites. PK assessments will continue to be optional except in the case of suspected hypersensitivity/anaphylactic reactions (see [Section 6.2.4.2.3](#) for more detail). Plasma samples will be collected for estimates of PK parameters using population PK and exposure-response analysis, if possible, according to the SOA in Appendix 2. A specialty laboratory will measure plasma pamrevlumab levels using a validated assay. For the population PK analysis, it is critical to accurately record the dosing time and date in addition to the sampling collection time and date. Both pre-dose and post-dose samples are required for PK. The pre-dose PK sample should be taken within 2 hours prior to dosing, the post-dose PK sample should be between 1-4 hours after the end of dosing.

6.2.4.2.2. Human Anti-Human Antibodies (HAHA)

Plasma samples will be collected for evaluation of human anti-human antibodies (HAHA) , in all subjects according to the SOA in Appendix 2. A specialty laboratory will measure HAHA titers using a validated assay.

Samples with positive HAHA results will be tested for neutralizing antibody (HAHA-NA) . The prevalence and duration of binding and neutralizing antibodies and the effect of these antibodies on the pharmacokinetics, pharmacodynamics markers, efficacy, and safety of pamrevlumab will be assessed.

6.2.4.2.3. Suspected Hypersensitivity or Anaphylactic Reactions

Any immunogenic reactions, including drug-related hypersensitivity or anaphylaxis, should have PK, HAHA, HAHA-NA, CTGF and tryptase drawn within 24 hours of a suspected reaction from pamrevlumab (see **Appendix 2** for more detail). This is in addition to timepoints in which PK, HAHA, and HAHA-NA and CTGF were drawn pre-infusion and post-infusion.

This will not be considered optional for the subject unless there is local institutional guideline consideration for total blood volume collection on the same day as a standard blood draw timepoint, which could preclude the subject from having this collection take place within 24 hours. The Tryptase sample should be drawn within 1 to 6 hours of immunogenic reaction, and all other samples should be collected within 24 hours of the immunogenic reaction. See **Appendix 2** for more detail.

6.2.4.2.4. Exploratory Biomarkers

Serum and plasma samples will be collected in all subjects according to the SOA in [Appendix 2](#). These samples will be stored and used to explore additional biomarkers of pamrevlumab's effects in the context of the current clinical trial.

Exploratory biomarkers to be analyzed may include markers of inflammation such as CRP, TNF, IL-6, IL-8 and CCL18; markers of fibrosis and collagen synthesis such as TGF-beta, PINP and PIIINP, as well as other markers of tissue remodeling and angiogenesis such as angiopoietins, VEGF, MMP7 and KL-6.

NOTE: Biomarker samples will be collected, except in countries where the Regulatory Agencies do not allow collection of these markers.

6.2.4.2.5. DNA for Genomic Analysis (Optional)

A genome-wide association study was performed in subjects with fibrotic idiopathic interstitial pneumonias (N = 1616) and controls (N = 4683) ([Fingerlin, 2013](#)) and determined an association of disease with TERT and MUC5B on chromosomes 5p15 and 11p15, respectively, the chromosome 3q26 region near TERC, and identified 7 novel chromosome loci. The novel loci include FAM13A (4q22), DSP (6p24), OBFC1 (10q24), ATP11A (13q34), DPP9 (19p13), and chromosomal regions 7q22 and 15q14-15. Their findings indicate that genes involved in host defense, cell-cell adhesion, and DNA repair contribute to the risk of fibrotic pulmonary disease. In this study, we plan to collect whole blood samples to isolate patient DNA and evaluate the relationship between clinical response to pamrevlumab and variants in loci such as those described above.

A whole blood sample will be collected for DNA analysis on Day 1 before dosing for all subjects who agree to DNA analysis. This testing is optional, requires specific consent by participating subjects and subjects may refuse DNA testing. Only tests for genetic loci associated with ILD, fibrosis or CTGF biology will be performed and all samples will be destroyed after testing is completed.

NOTE: DNA samples for genomics analysis will be collected for subjects who consent, except in countries where the Regulatory Agencies do not allow collection of these samples.

6.2.5. High Resolution Computerized Tomography (HRCT) Scans and Spirometry

The key study procedures that measure efficacy are serial spirometries to assess lung function (refer to the PFT Procedure Manual for additional details) and serial HRCT assessments to evaluate fibrosis. These measurements will be performed in all patients according to the SOA in [Appendix 1](#).

HRCT:

An Independent Radiology Review Group is assessing all HRCTs for:

- Quantitation of fibrosis, a secondary efficacy measure, and
- Confirmation of HRCT-related eligibility, specifically:
 - o Inclusion # 4
 - o Exclusion # 2

Assessment of UIP pattern. For the screening HRCT, the Independent Radiology Review Group is providing their assessment to study sites, in accordance with the Independent Radiology Review Imaging Charter. It is the responsibility of the Investigator to review this assessment prior to randomization, to make sure all HRCT-related eligibility criteria are met.

For the screening HRCT: if a recent scan, i.e., within 3 months prior to screening, is available, it can be utilized as the screening HRCT, provided it is submitted and evaluated by the Independent Radiology Imaging Review Group, is adhering to the same imaging acquisition parameters detailed in the Imaging Core Manual (ICM), and is either using the same accredited scanner, or is performed using the same modality, as the on-study HRCT scans.

Spirometry:

Subjects must have an FVCpp value >45% and <95% at screening **and** Day 1 (prior to randomization), in order to be eligible for the study.

For the screening FVCpp value and GAP score calculation: the quality-controlled, Best-Test Review (BTR) assessment provided by the spirometry vendor over-reader, which is provided to sites within 48 hours after uploading the test, is to be used for eligibility assessment and GAP score calculation.

For the Day 1 (pre-randomization) FVCpp value: the real-time value obtained from the device is to be used for eligibility confirmation, without the need to wait for the BTR assessment.

BTR assessments of all spirometries are conducted for statistical purposes, and will be provided to the site, for quality feedback.

NOTE: For spirometries deemed “unacceptable” by the spirometry vendor over-reader, the test has to be repeated.

6.2.6. Patient Reported Outcomes (PROs)

Patient reported outcome (PRO) data will be collected in all subjects to evaluate specific patient reported symptoms, treatment related symptoms and functional impacts that may be responsive to treatment. All questionnaires will be administered as specified in the SOA (see Appendix 1)

in the same order at Week 48 as was done at baseline. On weeks where both questionnaires and spirometry are performed, the PFT should be completed prior to administering the PRO.

6.2.6.1. St. Georges Respiratory Questionnaire (SGRQ)

The St. Georges Respiratory Questionnaire is a disease-specific instrument designed to measure impact on overall health, daily life, and perceived well-being in patients with obstructive airways disease.

6.2.6.2. University of California, San Diego – Shortness of Breath Questionnaire (UCSD-SOBQ)

The UCSD-SOBQ is a self-administered rating of dyspnea associated with activities of daily living (ADLs). The questionnaire is designed to assess severity of shortness of breath during specific ADLs and to assess the limitations due to shortness of breath, fear of harm from overexertion and fear of shortness of breath.

6.2.6.3. Leicester Cough Questionnaire (LCQ)

The Leicester Cough Questionnaire is a self-administered instrument designed to monitor individual patients cough, assess different aspects of health affected in patients and detect changes in health status within an adult chronic cough population ([Birring, 2003](#)).

7. ASSESSMENTS OF SAFETY

7.1. Background

Adverse event reports from Investigators are the critical building blocks to the development of the safety profile of the Study Drug. Subjects will be asked non-leading questions in general terms to determine the occurrence of AEs, according to the schedule outlined in [Appendix 1](#). In addition, all AEs reported spontaneously during the course of the study will be recorded. The Investigator must immediately (within 24 hours of awareness) report to the Sponsor or designated safety management vendor all SAEs, regardless of whether the Investigator believes they are related to the study drug.

7.2. Definitions

7.2.1. Definition of an Adverse Event (AE)

An adverse event is defined as any untoward medical occurrence in a clinical trial subject. The event does not necessarily have a causal relationship with study treatment. The Investigator is responsible for ensuring that any adverse events observed by the Investigator or reported by the subject as defined in the study protocol are recorded in the subject's medical record. The definition of adverse events includes worsening of a pre-existing medical condition. Worsening indicates that the pre-existing medical condition (e.g., diabetes, migraine headaches and gout) has increased in severity, frequency, and/or duration, and/or has an association with a significantly worse outcome. A pre-existing condition that has not worsened during the study or involves an intervention, such as elective cosmetic surgery, or a medical procedure while on study, is not considered an adverse event.

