7.2.2. Definition of a Serious Adverse Event (SAE)

A serious adverse event is any adverse event or suspected adverse reaction that results in any of the following outcomes:

- Death,
- A life-threatening AEs (i.e., if in the view of the Investigator or Sponsor, the subject was at immediate risk of death at the time of the event). Life-threatening does not refer to an event which hypothetically might have caused death if it were more severe,
- Inpatient hospitalization or prolongation of existing hospitalization,
- A persistent or significant incapacity or substantial disruption of the ability to conduct normal life functions,
- A congenital anomaly or birth defect, or
- Is considered a medically important event not meeting the above criteria, but which may jeopardize a subject or may require medical or surgical intervention to prevent one of the other criteria listed in this definition. Examples of such medical events include allergic bronchospasm requiring intensive treatment in an emergency room or

at home, and blood dyscrasias or convulsions that do not result in inpatient hospitalization.

Please note that death is an outcome, not an event; the primary cause of death would be the adverse event.

Surgical procedures, per se, are not SAEs. The condition requiring the surgical procedure, however, may be a SAE.

Scheduled or pre-planned hospitalization or prolongation of a hospitalization due to standard of care assessments and procedures (including elective procedures) do not warrant reporting as adverse events unless resulting observations are deemed by the Investigator to meet the definition of an adverse event.

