6.8.1. Adverse Events (AEs)

Adverse events will be coded using MedDRA.

A new or worsening AE occurring on or after the first dose of study drug and within 60 days after the last dose of study drug is defined as a treatment-emergent adverse event (TEAE). AEs that started after 1st dose in the OLE period will be excluded from the main study. Partially or incompletely missing AE start/stop date/time will be imputed (Appendix 1).

If more than one event occurs with the same system organ class (SOC) and preferred term (PT) for the same patient, the patient will be counted only once for that preferred term using the most severe and most related occurrence for the summarization by common terminology criteria for adverse events (CTCAE) severity grade and relationship to the study treatment. Relationship to study treatment will be imputed as "Related" for any TEAE with a missing value for relationship.

The cumulative incidence of the following AE categories including the number (%) of subjects will be produced:

- Summary of all AEs
- TEAEs by PT
- TEAEs by SOC and PT
- TEAEs by SOC, PT, and maximum severity
- TEAEs by SOC, PT, and investigator-determined relationship
- TEAEs with severity grade \geq 3 by SOC and PT
- TEAEs related to study treatment determined by the investigator by SOC and PT
- TEAEs with frequency \geq 5% of subjects in either treatment arm by SOC and PT

Confidential Page 31 of 56

- Non-serious TEAEs with frequency ≥ 5% of subjects in either treatment arm by SOC and PT (Note: this is required for ClinicalTrials.gov)
- TEAEs leading to discontinuation of study treatment by SOC and PT
- TEAEs leading to interruption of study treatment by SOC and PT
- Treatment-emergent serious AEs (TESAEs) by SOC and PT
- TESAEs by PT
- TESAEs by SOC, PT, and maximum severity
- TESAEs related to study treatment determined by the investigator by SOC and PT
- Fatal TESAEs (i.e., adverse events that have an outcome of death) by SOC and PT
- All-cause deaths

Listings of all adverse events, TESAEs, TEAEs leading to study treatment discontinuation, TEAEs leading to death, and all-cause deaths will be provided.

In addition, TEAEs and TESAEs will be presented by subgroups as described in Section 6.7.1.4 along with an additional subgroup assessment by concomitant steroid medication use.

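### As drafted, the last sentence of the AE definition (Protocol 7.2.1) excludes a pre-existing condition that worsens and needs a procedure, contradicting the same paragraph and 7.2.2

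*Protocol*

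**What the plan says.** Section 7.2.1 of the protocol starts broadly: "An adverse event is defined as any untoward medical occurrence in a clinical trial subject". It continues: "The definition of adverse events includes worsening of a pre-existing medical condition". Worsening means that the condition "has increased in severity, frequency, and/or duration, and/or has an association with a significantly worse outcome". No exception is made for conditions that need treatment or a procedure.

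The last sentence of the section then states what falls outside the definition. It applies to any pre-existing condition that fits these words: "that has not worsened during the study or involves an intervention, such as elective cosmetic surgery, or a medical procedure while on study". The sentence closes with the consequence: "or a medical procedure while on study, is not considered an adverse event".

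Section 7.2.2 makes a serious adverse event a kind of adverse event or suspected adverse reaction. It separates a surgical procedure, which is not itself serious, from the reason for it: "The condition requiring the surgical procedure, however, may be a SAE".

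The double-blind SAP, Section 6.8.1, builds the treatment-emergent definition on the protocol's: "A new or worsening AE occurring on or after the first dose of study drug", up to 60 days after the last dose. It has no exception for procedures.

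**The concern.** The exclusion sentence offers two alternatives, and either is enough. The second, that the condition involves an intervention or a medical procedure on study, does not require the condition to be stable. Elective cosmetic surgery is given only as an example of an intervention, and the words about a medical procedure carry no limit to elective or planned ones. So the sentence appears to remove something that the same paragraph has just included.

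This is the definition that sites apply when they decide what to record, and the AE tables rest on it. IPF is a pre-existing condition in every subject, so the conflicting case is not remote. The schedule of assessments for the open-label extension (Appendix 6) refers to Section 7 for its safety assessments, and that phase has long-term safety as its objective, so the same wording governs it. What is at stake is consistent AE and SAE reporting across sites: one investigator can follow the worsening sentence and another the exclusion sentence, and both comply with the text.

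**Working it through.** The plan gives no figure on this point, so there is nothing to reproduce. The check sets the sentences against each other.

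**Step 1. Parse the exclusion.** A pre-existing condition is excluded if (A) it has not worsened, or (B) it involves an intervention or a medical procedure on study.

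**Step 2. Apply both sentences of 7.2.1 to the four possible cases.**

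| Pre-existing condition | Procedure on study | Worsening sentence | Exclusion sentence (A or B) | Conflict |
|---|---|---|---|---|
| Not worsened | No | Does not apply | Excluded (A) | No |
| Not worsened | Yes | Does not apply | Excluded (A and B) | No |
| Worsened | No | AE | Not excluded | No |
| Worsened | Yes | AE | Excluded (B) | **Yes** |

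Only the fourth case conflicts. Limb B does work of its own only there, because in the second case limb A already excludes the condition.

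**Step 3. Try the alternative grammar.** Could the negation cover both limbs, so that a condition is excluded only if it has neither worsened nor involved a procedure? The present-tense verb in the second limb does not fit that reading. It would also take a stable condition with elective cosmetic surgery out of the exclusion, which defeats the purpose of the example.

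**Step 4. Compare with the rest of the plan.**

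- Section 7.2.2: the condition that requires surgery may be an SAE. If that condition is pre-existing and has worsened, limb B says it is not an AE, so it could not be an SAE by way of being an AE.
- Section 7.3.2: laboratory changes that need treatment are AEs. There, need for intervention brings a finding in rather than taking it out.
- Section 7.3.4: the guidance on events not related to study drug refers to underlying disease that has not worsened, and has no limb on procedures.
- SAP 6.8.1: new or worsening AEs count as treatment-emergent, with no exception for procedures.

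All four agree with the worsening sentence. Limb B is the outlier.

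**Step 5. Test the obvious repair.** If the procedure wording applied only to conditions that have not worsened, the fourth row would read as an AE under both sentences, the other rows would not change, and the conflict would be gone.

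**The case against.** The best defence is that no sensible reader would apply limb B literally. The rest of Section 7 treats the need for intervention as a feature of adverse events. Hospitalization, or its prolongation, is a seriousness criterion in 7.2.2, and an event that may need medical or surgical intervention can be medically important. In 7.3.2, other treatment required is an attribute to be recorded for each AE. In 7.3.3, the descriptions of Grades 2 and 3 refer to intervention. The only example in the disputed sentence is elective cosmetic surgery. The likely intent is therefore that a stable condition does not become an AE because a planned procedure is done for it.

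Most of this stands. It shows a drafting slip rather than a deliberate design choice, and it is a good reason to expect that many sites would report correctly. It does not remove the contradiction. The grading and attribute rules describe events already accepted as AEs, so they do not override a sentence saying that a condition is not one. The exception in 7.2.2 for planned hospitalization is lifted only where findings meet the AE definition, which leads back to the sentence in question.

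The defence is also right that limb B is limited in scope, because it covers pre-existing conditions only. Section 2.2 describes an acute exacerbation of IPF as an acute deterioration with a new widespread alveolar abnormality, which an investigator could well regard as a new event. A new infection that leads to hospital admission is not a pre-existing condition either.

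**Conclusion.** The sentence is wrong as written. It contradicts the worsening rule in its own paragraph and cannot be squared with 7.2.2 for a worsened pre-existing condition that needs surgery. It has no bearing on sample size, power or alpha. The possible consequence is inconsistent AE and SAE classification between sites, of a size that the documents do not allow to be estimated. The conclusion rests on the wording alone and assumes only that some sites may apply the last sentence literally.

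A reader might infer three stronger points. The documents do not support them.

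- **A count of lost events.** In the Phase 2 placebo-controlled study (Protocol 2.6.3), 5 of 50 and 7 of 53 subjects were hospitalized following a respiratory TESAE: (5 + 7)/(50 + 53) = 12/103 = 11.7%. Those events were reported, so they show an event rate, not under-reporting. They are not divided into worsened IPF and new illness, and the share involving a procedure is not given. No count for this trial follows.
- **Loss of adjudicated endpoint events.** Appendix 1 has no separate row for exacerbations or respiratory hospitalizations, so a link through AE reporting is conceivable. But SAP 6.7.2.1.5 says that the adjudication charter pre-defines which exacerbation events are adjudicated, and neither the charter nor the case report form is among the documents. Appendix 1 also has its own row for procedures and nondrug therapies, separate from Adverse Events. An effect on the endpoints is not shown.
- **A second fault in 7.2.2.** That section exempts "Scheduled or pre-planned hospitalization or prolongation of a hospitalization due to standard of care assessments and procedures". The opening qualifier can naturally be read as covering prolongation too, and the sentence keeps a safeguard for findings that meet the AE definition. It needs no rewriting of its own once that definition is repaired.

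**What to change.** Reconcile the last sentence of 7.2.1 with the rest of that section and with 7.2.2. One wording that does so:

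*A pre-existing condition that does not worsen on study is not an adverse event, even if a planned or elective procedure for it takes place on study. If a pre-existing condition, IPF included, worsens, this is an adverse event whatever intervention or procedure it requires.*

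This keeps what the sentence was probably meant to do and removes the only conflicting case. It changes a reporting definition, not treatment or clinical management.

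The cost is one protocol sentence replaced by two, and a short clarification letter to sites. Section 7.2.2 and SAP 6.8.1 can stay as they are. Some additional events may be reported.
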